Study Design Overview: We propose to study the separate and combined effects of the FDA-approved cannabinoid dronabinol (Marinol) and the prototypical opioid hydromorphone (Dilaudid). Following telephone and screening to establish study eligibility, a cohort of **n=100** adults with knee osteoarthritis (KOA) will complete four different within-subject experimental sessions. Participants will complete one of two Phases, receiving either a 4mg or 2mg dose of hydromorphone. Randomization will be split equally across the two Phases. During each session, participants will complete baseline QST, questionnaires, and a neurocognitive battery. Oral hydromorphone will be administered in the first session. Subsequent sessions will consist of 1 of 3 conditions, and session order will be randomized and counter-balanced. Conditions will be 1) placebo; 2) oral dronabinol (10mg); and 3) combined hydromorphone and dronabinol (10mg). Measures will be repeated throughout the session to fully characterize the drug effects. Participants and staff will be kept blinded to the study medications under investigation, and participants will be informed in the consent form they may receive a combination of FDA-approved stimulants, benzodiazepines, opioids, cannabinoids, over-the-counter medications or placebo, though the participants will not actually be receiving stimulants, benzodiazepines, or over-the-counter drugs. All participants will be provided with transportation to and from the experimental sessions. Primary outcomes are measures of clinical pain, central sensitization, physical function and drug effects/adverse events. A subset of participants will undergo blood draws for pharmacokinetic (pK) profile. This will be voluntary and should aid recruitment as those that do not want an IV will still be allowed to participate in the study. We will aim to recruit 30 participants that volunteer to undergo IV/blood drawing procedures in order to characterize pK.

Phase 1: The initial Phase of this project will include hydromorphone at a dose of 4mg.

Phase 2: The second Phase of this project will include hydromorphone at a dose of 2mg in order to evaluate drug effects at a reduced opioid dose.

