a. Primary outcome variable:

Aim 1: Evaluate the magnitude and duration of cannabinoid/opioid combination to reduce clinical pain (Hyp1) and central sensitization (Hyp2). Hyp1 (pain VAS) and Hyp 2 (CS) will be analyzed using repeated 2-factor (Drug x Time) models that examine linear and quadratic effects as well as duration and magnitude, and direct and interaction effects. If large variation exists across subjects at baseline, then raw data will be transformed to change-from-baseline and analyzed in drug condition by time models. A secondary outcome will be peak change from baseline, analyzed as a function of Drug (1-factor model).

- Aim 2: Evaluate the degree to which physical functioning is altered by the cannabinoid/opioid combination.** Hyp3 will be assessed using the TUG and 6MWT. Time to complete the TUG task will be the primary outcome and will be evaluated using 2-factor (Drug x Time: Pre to Peak) models.
- Aim 3: Conduct a direct comparison of the subjective, physiological, abuse liability, and cognitive effects of the cannabinoid, opioid, and combination.** Hyp4 (adverse events) will be assessed by summing the mean number of related mild, moderate, and severe adverse events (separately) and using 1 factor models to assess a main effect of Drug. Hyp5 (abuse liability) will be assessed using the Drug vs. Money questionnaire and changes in VAS ratings using 2-factor models (Drug x Time). Hyp6 will evaluate changes in neurocognitive performance, including study session number as a covariate to control for practice effects, using 2-factor (Drug x Time) analyses. Secondary outcomes for this hypothesis will be analysis of peak change from baseline for the cognitive outcomes, analyzed using 1-factor (Drug) ANOVAs to evaluate a main effect of drug.

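### Session is adjusted for only in the cognition analysis (Hyp6); adding a session term for sessions 2-4 to Hyp1, Hyp2, Hyp3 and Hyp5 would protect the precision of the three randomised contrasts at almost no cost

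*Combined protocol and SAP*

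**What the plan says.** All references are to the combined protocol and SAP.

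- **Design (section 4.a, Study Design Overview).** "Oral hydromorphone will be administered in the first session". The other three conditions follow in sessions 2-4, and "session order will be randomized and counter-balanced".
- **Aim 1 (section 7.a).** "Hyp1 (pain VAS) and Hyp 2 (CS) will be analyzed using repeated 2-factor (Drug x Time) models". Change scores are conditional: "If large variation exists across subjects at baseline, then raw data will be transformed to change-from-baseline". Peak change is a secondary outcome with Drug as the only factor.
- **Aim 2 (section 7.a).** "Time to complete the TUG task will be the primary outcome and will be evaluated using 2-factor (Drug x Time: Pre to Peak) models"; no session term is named.
- **Aim 3 (section 7.a).** Hyp5 uses the Drug vs. Money questionnaire and changes in VAS ratings in Drug x Time models, with no session term. For cognition the plan differs: Hyp6 is analysed "including study session number as a covariate to control for practice effects".
- **General model (end of section 7.a).** Multilevel models are fitted separately by Phase, with AR1 or compound-symmetry covariance and Tukey comparisons. Section 7.b adds sex and characteristics that differ by sex. Neither names a session or period term.

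**The concern.** The plan accepts that performance may change from visit to visit, but allows for it in one family of outcomes only. Section 4.a has the cognitive tasks trained to stability at screening, and they still receive the covariate. Training on the pain tests is to be done at screening where possible, none is described for Timed Up and Go, and neither has a session term. The plan gives no reason for the difference.

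Counterbalancing makes a session trend average out across drugs, so the contrasts among placebo, dronabinol and the combination are not biased by it in balanced data. It does not remove the trend from the data. Without a session term the trend counts as unexplained within-person variation. The covariance structure does not help, because AR1 and compound symmetry describe correlation and not a shift in means. Standard errors would then be overstated and power lost for two comparisons that the Aim 1 and Aim 2 hypotheses need: combination against dronabinol and combination against placebo.

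**Working it through.** **The plan's own figures.** The documents give no drift estimate and no within-person SD, so there is no stated figure to reproduce on this point. The one design figure is 10-15 participants for large effects (section 7.c). It is plausible: a paired t-test with an assumed d = 0.8 needs 15, and a four-condition repeated-measures F-test with an assumed f = 0.4 needs 10 at correlation 0.5 or 14 at 0.3. Nothing below rests on it.

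**Set-up.** One value per participant per session; four conditions; hydromorphone alone fixed in session 1; the other three in balanced orders over sessions 2-4; within-person SD of 1; linear drift of d SD per session (an assumption). Participants and drug are in the model. n is the number per Phase: 50 if the 100 in section 4.a are split equally, 32 if the 64 completers in section 7.c are.

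**Residual variance without a session term.**
- Around their own mean, sessions 2, 3 and 4 deviate by -d, 0 and +d. That adds 2d² to each participant's residual sum of squares, or 2nd² in total.
- Residual degrees of freedom are 3(n-1).
- Expected residual variance is therefore 1 + 2nd²/[3(n-1)], or about 1 + (2/3)d². With a session term it is 1.

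**Standard-error excess at n = 30** (n/(n-1) = 1.034):

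| d | residual variance | square root | SE too large by |
|---|---|---|---|
| 0.25 | 1.043 | 1.021 | 2% |
| 0.5 | 1.172 | 1.083 | 8% |
| 0.75 | 1.388 | 1.178 | 18% |
| 1.0 | 1.690 | 1.300 | 30% |

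Simulation at n = 50 agrees. The 95% interval for combination vs placebo is 0.807 SD wide without the term and 0.790 with it at d = 0.25 (ratio 1.02), and 0.854 against 0.789 at d = 0.5 (ratio 1.08).

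**Power and type I error** (one two-sided 5% comparison, before Tukey adjustment). With balanced orders the estimate is the same with or without the term; only its reported SE changes, by the factor k in the third column. If the adjusted test has 80% power, the unadjusted test has about Φ(2.80 - 1.96k):
- k = 1.083: Φ(0.68) = 75%
- k = 1.178: Φ(0.49) = 69%
- k = 1.300: Φ(0.25) = 60%

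Simulations gave about 76%, 69-70% and 60-62%. Type I error falls to about 3.4%, 2.4% and 1.2%. At d = 0 the term costs essentially nothing.

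**Uneven orders.** Thirty-two participants fill six orders five times, with two left over. The position difference between two given conditions is +2, +1, +1, -1, -1 or -2 sessions across the six orders. Two different extra orders add at most 2 + 1 = 3, so the contrast shifts by at most 3d/32 = 0.094d. The mean absolute shift over the 15 possible pairs is 20/15/32 = 0.042d, and the expected shift is zero.

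**Hydromorphone alone.** Session 1 lies 2d below the mean of sessions 2-4 (d, 2d and 3d above session 1, mean 2d). Combination minus hydromorphone alone is therefore biased by 2d without a session term: 0.50 SD at d = 0.25 and 1.0 SD at d = 0.5. A categorical term coded to sum to zero over sessions 2-4 and zero in session 1 leaves this estimate, and its bias, as they are. A linear session number removes the bias only if drift is linear from session 1, and at d = 0.25 and n = 50 it widens that interval from 0.807 to 1.123 SD (39%).

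**The case against.** **Daily baselines.** This is the strongest objection. Pain testing has a pre-dose baseline on every session day, physical tests are done at baseline and projected peak, and Hyp5 uses changes in VAS ratings. A session shift common to pre- and post-dose values cancels in change-from-baseline and Drug x Time contrasts. This stands, and it limits the gain. It does not remove it: Aim 1 turns to change scores only if baseline variation is large, Drug main effects on raw data keep the shift, drift in the drug response itself does not cancel, and the Drug vs. Money questionnaire is completed only at the day's final assessment and so has no baseline.

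**Size of drift.** The larger losses need 0.5-1.0 SD per session, or 1-2 SD between sessions 2 and 4. The documents support no such value, and session 1 already serves as a full exposure before any randomised session. This stands; at 0.25 SD the cost is 2%.

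**Stronger readings that the documents do not support.**
- A reader might infer that all intervals for these outcomes are too wide. Three of the six pairwise contrasts involve hydromorphone alone, where the problem is confounding with session and the planned interval is mis-centred.
- A reader might treat the study as a three-treatment, three-period crossover and obtain a variance factor of 1 + d², with SEs 3%, 12%, 25% and 41% too large. The plan compares four conditions in each Phase (Tables 1a and 1b), so session 1 contributes to the residual and dilutes the effect.
- A reader might want to replace the Hyp6 covariate as well. Hyp6 compares with the opioid alone, and under linear drift the sum-to-zero coding would turn a bias of about zero into 2d.
- A reader might infer a risk of false positives. For the randomised contrasts in balanced data the tests become conservative.

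**Conclusion.** The omission is clear from the text, and so is its direction. Without a session term, drift over sessions 2-4 inflates the standard errors for combination vs dronabinol, combination vs placebo and dronabinol vs placebo in Hyp1, Hyp2, Hyp3 and Hyp5. How much this matters depends on a drift that the documents do not quantify: negligible at 0.25 SD per session, appreciable only from about 0.5 SD, and reduced wherever the analysis works on change from the same day's baseline. Uneven orders add a shift of at most about 0.1d. The percentages rest on linear drift, one value per session, a pooled residual and four conditions. This is a precision refinement to consider. It does not threaten the validity of the randomised comparisons, and it leaves open the separate confounding of hydromorphone alone with session 1.

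**What to change.** - Add a categorical session effect to the Hyp1, Hyp2, Hyp3 and Hyp5 models, coded to sum to zero over sessions 2-4 and set to zero in session 1. Report the three randomised contrasts from these models.
- Leave the Hyp6 session-number covariate as planned.
- State that contrasts with hydromorphone alone are non-randomised and remain confounded with session. With balanced orders the new term leaves their point estimates unchanged. Their intervals may tighten a little through the pooled residual, which must not be read as a repair.

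The cost is one line in the plan and two degrees of freedom, with no new data and practically no loss if there is no drift.

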
2. Objectives (include all primary and secondary objectives)

Aim 1: Evaluate the magnitude and duration of cannabinoid/opioid combination to reduce clinical pain and central sensitization. We hypothesize the cannabinoid/opioid combination will increase the

magnitude and duration of analgesia in clinical pain report (Hyp1) and QST-derived central sensitization (Hyp2), relative to each drug administered alone and relative to placebo.

Aim 2: Evaluate the degree to which physical functioning is altered by the cannabinoid/opioid combination. We hypothesize that the drug combination will improve physical function (Hyp3) relative to the drugs administered alone and placebo.

Aim 3: Compare the subjective, physiological, abuse liability, and cognitive effects of the cannabinoid, opioid, and combination. We hypothesize that cannabinoids will not increase adverse events (Hyp4), or abuse liability (Hyp5: ratings of positive drug effects) relative to opioids alone and that the cannabinoid (alone and in combination with opioids) will reduce neurocognitive performance (Hyp6), relative to the opioid alone and placebo.

Aim 4: Evaluate the pharmacokinetic and pharmacodynamic profile of the cannabinoid, opioid, and the combination in OA patients. We hypothesize that the combined dose will result in an altered pharmacokinetic (Hyp7) /pharmacodynamics profile (Hyp8) compared to either drug alone.

3. Background (briefly describe pre-clinical and clinical data, current experience with procedures, drug or device, and any other relevant information to justify the research)

This laboratory study is the first step in addressing an important and timely public health problem: Can cannabinoids enhance the analgesic efficacy of an opioid and ultimately reduce opioid dosing in people with chronic pain?

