| Randomized Order | | |
| 2 | 0 (placebo) | 0 (placebo) |
| 3 | 0 (placebo) | 10mg |
| 4 | 4mg | 10mg |

approximately 0930 participants will complete baseline QST, physical functioning measures, and self-report measures (see below). The second 10-14mL blood draw (for those in the pK group) will be collected and then two oral capsules containing either active drug or placebo (randomized in sessions 2-4) will be administered at approximately 1100. Briefly, subjects will complete QST, physical functioning, cognitive testing, self-report, and vital sign measures (as well as blood draws for those in the pK group) at regular intervals following study drug administration. Self-report measures will include specific opioid agonist and antagonist effects, to assess whether cannabinoids

are exerting an effect on a particular category of opioid agonist symptom, and will capture whether any negative effects (e.g., nausea) occur. Frequent collection will enable evaluation of time to peak drug effects, duration of effects, and general time course of effects and is a widely used and accepted approach in laboratory studies of drug effects. During the final assessment each day, subjects will complete a Drug vs. Money Questionnaire to indicate the dollar value they would place upon the drug received⁹⁸, which is a well-accepted proxy measure of abuse liability. Study staff will document adverse events throughout the study and any subject who experiences a strongly unpleasant effect of the medications, or wishes to discontinue for any reason will be able to end participation at any time. Any subject who is experiencing strong agonist effects at the end of the session will be provided overnight accommodation in the Clinical Research Unit (CRU; which is located on our campus and with whom we have frequent collaborations); based on our experience we expect this to be rare and are budgeting for 20% of sessions to undergo a one-night CRU stay.

Measures

Pilot testing indicates it takes approximately one hour to complete the assessment battery (see Table 2).

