dronabinol reaches peak concentrations in 2-4 hours and is 90-95% absorbed but, due to extensive first-pass metabolism, is only 10-20% bioavailable. It is excreted in fecal (35-50%) and renal (10-15%) waste. The elimination half-life is biphasic, with an initial half-life of 4 hours and a terminal half-life of 25-36 hours, and an active metabolite (11-hydroxy-delta-9-THC) is produced. There is no current evidence that dronabinol is differentially affected by P450 status. Dronabinol is sold commercially in 2.5mg, 5mg, and 10mg dose ranges. **We have chosen to administer a 0 mg (placebo) and 10mg dose of dronabinol in this study**, which is within the range currently prescribed for chemotherapy-induced nausea and vomiting and AIDS-related anorexia, and therefore will have direct clinical applicability. Dronabinol will be purchased as a capsule and will be over-encapsulated by our research pharmacy to ensure double-blind administration procedures. Placebo doses will consist of lactose or another benign weight-matched filler.

Pharmacokinetic (pK) Analyses: Blood samples, drawn on a subset of participants, will enable direct comparison of serum drug levels with outcomes for the study aims (e.g., analgesia and physical functioning, subjective and observer- rated effects, abuse liability measures, and cognitive performance). We have chosen to sample pK at numerous timepoints to examine whether the duration of effects changes as a function of drug administration and determine whether behavioral changes following hydromorphone/dronabinol co-administration result from pharmacological enhancement or whether co-administration modifies the metabolic profile of either drug in such a way that it changes their duration of action. pK analysis is considered critical for this initial stage of evaluating drug-drug interactions¹³⁵ and will directly inform decisions regarding specific opioid/cannabinoid dose combinations that may be most appropriate to advance into clinical trials for the treatment of pain.

- b. Justification and safety information if FDA approved drugs will be administered for non-FDA approved indications or if doses or routes of administration or participant populations are changed.

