- Aim 4: Evaluate the pharmacokinetic (pK) and pharmacodynamic (pD) profile of the cannabinoid, opioid, and the combination in OA patients.** Hyp 7 (pK) will be assessed by evaluating Cmax (maximum concentration) and Tmax (time to maximum concentration) as a function of Drug condition using 1-factor models. We will also examine linear and quadratic effects to evaluate the time course of concentration. Linear and quadratic effects will be modeled for Hyp8 (pD) and analyzed by evaluating VAS and physiological ratings, transformed to change from baseline, evaluating area under the curve and peak change from baseline to identify main effects of the Drug condition. We will then conduct multivariate regression analyses to evaluate the degree to which the Cmax and Tmax correlate with pharmacodynamic outcomes, including abuse liability ratings, VAS ratings of drug effects, and cognitive testing outcomes.

Statistical analyses will be conducted separately by Phase and use multilevel analyses with an autoregressive (AR1) or compound symmetry (CS) covariance structures (as appropriate for the data set) using SAS PROC MIXED¹³⁷. Interpretation of drug condition main effects and interactions will rely on Tukey post-hoc tests. Statistical significance will be set at $p < 0.05$.

Expected Outcomes: We expect that dronabinol will enhance hydromorphone-induced analgesia to both clinical and laboratory-evoked pain. Our comprehensive battery of rigorous, testing procedures provides an opportunity to test effects on multiple mechanisms of experimentally-induced pain. We also expect improvement in physical functioning under combined dosing, and that the addition of the cannabinoid will not significantly increase the overall abuse liability or adverse event profile. We do suspect the cannabinoid may have cognitive effects (though the degree to which this may happen is not clear).

b. Secondary outcome variables.

Demographic and drug use characteristics that are hypothesized a priori to be associated with outcomes (e.g., Body Mass Index) will be compared across sex groups and significant differences will be included as covariates in the subsequent analyses. All analyses will be repeated and sex (male/female) will be added as a factor to the analyses.

c. Statistical plan including sample size justification and interim data analysis.

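### The pK analysis names no AUC or half-life for concentrations, so a change in systemic elimination, chiefly of hydromorphone, could go largely unseen

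*Combined protocol and SAP*

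**What the plan says.** Section 2, Aim 4, sets the hypothesis: "We hypothesize that the combined dose will result in an altered pharmacokinetic (Hyp7) /pharmacodynamics profile (Hyp8) compared to either drug alone". The pharmacokinetic paragraph of section 6 gives the purpose of sampling, which includes learning "whether co-administration modifies the metabolic profile of either drug in such a way that it changes their duration of action". It adds that the results will guide which dose combinations go forward to clinical trials.

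Section 7a, Aim 4, gives the analysis: "Hyp 7 (pK) will be assessed by evaluating Cmax (maximum concentration) and Tmax (time to maximum concentration) as a function of Drug condition", by one-factor models. It continues: "We will also examine linear and quadratic effects to evaluate the time course of concentration". Area under the curve appears in the same paragraph, but only for the drug-effect and physiological ratings of Hyp8 ("evaluating area under the curve and peak change from baseline"). No AUC, half-life or clearance is named for concentrations, and the later pK-pD regressions also use only Cmax and Tmax.

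The samples are serial. Section 4a (Experimental Sessions) has draws before dosing and at intervals afterwards, and section 6 says "We have chosen to sample pK at numerous timepoints". The draw times and the last sample are not visible in the text available. Tables 1a and 1b give hydromorphone in conditions 1 and 4 and dronabinol in conditions 3 and 4.

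**The concern.** The question is about metabolism and duration; the named measures are the height and time of the peak. If clearance falls after absorption, the peak moves little and the main change is a slower decline, which appears in AUC and half-life. A real interaction could then be reported as no change in pK, and that result is meant to inform dose combinations.

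The one-factor Drug test raises a second problem. Each analyte is absent by design from two of the four conditions. In those sessions Cmax is at or near zero and Tmax has no meaning. A main effect over all four conditions says that people given a drug have it in their blood. The contrast that bears on Hyp7 is the combination against the same drug alone.

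**Working it through.** **1. The plan's own figure.** Section 7c says 10 to 15 people suffice for large effects at power 0.8 and alpha 0.05. The effect sizes used are not given. A two-sided paired t test (noncentral t, noncentrality d√n) needs n = 15 at d = 0.8 and n = 10 at d = 1.0, so the figure reproduces under the usual meaning of large. It is not specific to Cmax, Tmax or AUC.

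**2. Model.** One compartment, oral dose, scaled to FD/V = 1:

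- C(t) = ka/(ka − ke) × (e^(−ke·t) − e^(−ka·t)), with ke = ln 2 / half-life
- Tmax = ln(ka/ke)/(ka − ke), solved for ka
- AUC(0–T) = ka/(ka − ke) × [(1 − e^(−ke·T))/ke − (1 − e^(−ka·T))/ka]

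Halving systemic clearance halves ke and leaves ka unchanged.

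**3. Hydromorphone.** The documents give onset (15 minutes) and duration of effect (4 to 5 h, section 8a), but no half-life or Tmax. Assumed: half-life 2 to 3 h, Tmax 0.75 to 1.5 h, last sample at 8 h.

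Example with half-life 2 h and Tmax 1 h: ke = 0.347, ka = 2.19. Halving ke moves Cmax from 0.707 to 0.804 (×1.14), Tmax from 1.00 to 1.26 h, and AUC(0–8) from 2.67 to 4.20 (×1.57).

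| Clearance | Cmax | Tmax | AUC(0–8 h) |
|---|---|---|---|
| −25% | +3% to +9% | +0.06 to +0.18 h | +17% to +24% |
| −50% | +7% to +20% | +0.15 to +0.45 h | +40% to +58% |

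With a 6 h window, halved clearance still raises AUC by 30% to 46%.

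**4. Dronabinol, systemic clearance only.** Section 6 gives Tmax 2 to 4 h, initial half-life 4 h and terminal half-life 25 to 36 h. Clearance halved, 8 h window:

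| Half-life | Cmax | AUC(0–8 h) |
|---|---|---|
| 4 h | +14% to +26% | +26% to +30% |
| 25 h | +2% to +5% | +5% |

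At half-life 4 h, Tmax 4 h and a 6 h window, Cmax moves more than AUC (+26% against +19%).

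**5. Dronabinol, first-pass metabolism included.** Section 6 gives 90% to 95% absorbed and 10% to 20% bioavailable. In a well-stirred liver model, the fraction escaping first pass is 1 − E = F/fa, and E = x/(1 + x), with x proportional to intrinsic clearance. For F = 0.10 and fa = 0.90: 1 − E = 0.111, so x = 8. Halving to x = 4 gives 1 − E = 0.20, so bioavailability is multiplied by 0.20/0.111 = 1.80 and systemic clearance by 0.80/0.889 = 0.90. Over the stated ranges of F and fa, with half-life 4 h, Cmax rises 71% to 88% and AUC(0–8) rises 77% to 90%.

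**6. Power.** Section 4a aims for 30 pK volunteers and section 7a analyses each Phase separately, so about 15 per Phase if they split evenly (assumed). With within-person CV 30% (assumed, the same for Cmax and AUC), the SD of a within-person log ratio is √(2 ln(1 + 0.3²)) = 0.415. The noncentrality is ln(ratio)/(0.415/√15) = ln(ratio)/0.107.

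| True ratio | Power, CV 30% | CV 20% to 40% |
|---|---|---|
| 1.10 | 13% | 23% to 10% |
| 1.20 | 35% | 65% to 23% |
| 1.50 | 94% | about 100% to 76% |

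These are two-sided paired tests at 0.05, without Tukey adjustment. The hydromorphone Cmax ratios in step 3 (1.07 to 1.20) fall in the first two rows or below. The AUC ratios (1.40 to 1.58) lie around the third.

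**The case against.** The strongest reply is that the plan does more than test a peak. The linear and quadratic terms address time course, which is what duration of action concerns, and they can pick up a slower decline. That stands in part: a reader who inferred that Hyp7 rests on Cmax and Tmax alone would be wrong. But a quadratic is a rough fit to an absorption-elimination curve and gives no exposure ratio.

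A reader might also infer that Cmax barely responds to any change in metabolism. The protocol's own bioavailability figures contradict this for dronabinol (step 5). Nor do the documents support an illustration in which halved dronabinol clearance doubles exposure: that is AUC to infinity, which a one-day session probably cannot estimate against a terminal half-life of 25 to 36 h. If hydromorphone has material first-pass extraction, which the documents do not state, its Cmax would respond more than in step 3.

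Finally, the plan does not say that undosed sessions enter the pK test. Hyp7 is framed against each drug alone, and section 7a interprets Drug effects by Tukey comparisons, which include the right pairs. So this part is conditional on a literal four-level test. Even then, four conditions give six pairwise comparisons, of which only one per analyte is relevant, and the adjustment for the rest costs power.

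**Conclusion.** The point holds in limited form. The plan asks about metabolism and duration but prespecifies no exposure or elimination measure for concentrations, although it uses AUC for the ratings in Hyp8. The loss is material for a change in systemic elimination of hydromorphone: a Cmax shift of 7% to 20% against an AUC shift of 40% to 58% when clearance halves. With 15 people, power is at most about 35% for the former, against 94% for a ratio of 1.50. For dronabinol, AUC over the session adds little to Cmax.

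These figures rest on an assumed hydromorphone half-life and Tmax, a last sample at 8 h, a CV of 30% and an even split of volunteers between Phases. The textual mismatch does not depend on them. The documents do not show that the current analysis would miss every metabolic interaction, or that undosed sessions will be included; they leave the second point open.

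**What to change.** In section 7a, Aim 4:

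- Add log AUC to the last common sampling time as a Hyp7 measure alongside log Cmax, and half-life where it can be estimated. Keep Tmax and the time-course terms.
- Report each as the within-person ratio with a confidence interval (a within-person difference for Tmax): hydromorphone in the combination versus hydromorphone alone, and dronabinol in the combination versus dronabinol alone.
- State that each analyte is analysed only in the two sessions in which it was dosed.
- State the sampling times and the last common time. Include the active dronabinol metabolite only if it is already assayed; section 6 mentions the metabolite but commits only to serum drug levels.

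This needs wording and a standard calculation on samples already planned. The cost is one more pK measure to report, and an AUC for dronabinol that is truncated and should be labelled so.
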